181 During a cardiac arrest, the brain is exposed to a variable period of hypoxaemia and ischaemia, which may result in
182 death or survival with cognitive deficits [7]. Six months after OHCA, cognitive deficits can still be detected in up to
183 half of all survivors [8]. Hypoxic-ischaemic brain injury also has an impact on other important aspects of life.
184 Survivors report symptoms of depression, dependency on others for daily functioning and a lower quality of life [9,
185 10]. Optimal CPR is one of the key factors associated with avoiding or minimising neurological impairment in the
186 survivors of OHCA, and early effective airway management is fundamental to this. Effective ventilation maintains
187 blood oxygenation, thereby reducing hypoxaemia and reducing the risk of brain damage [11, 12], and is associated
188 with both return of spontaneous circulation (ROSC) and neurological recovery following cardiac arrest[11]. This
189 increases the number of survivors and the quality of survival, with decreased dependency on acute and long-term care.
190 Importantly, however, efforts to secure effective ventilation should not prejudice the continuous chest compressions
191 that support the circulation and that are also essential for long-term survival.

192

193 Effective CPR with airway management improves survival and health related quality of life [13, 14]. The first few
194 minutes of CPR are critical; early ROSC is associated with better long-term neurological outcome[15, 16]. Traditional
195 teaching suggests that tracheal intubation (intubation) is the best way to manage the airway during OHCA [17].
196 However, this assumption has never been well tested [14], and pre-hospital intubation attempts by paramedics are
197 associated with important complications: interruptions in chest compressions, unrecognised oesophageal intubation,
198 compromised oxygenation and delays in accessing definitive care [18, 19].

199

200 Supraglottic airway devices (SADs) are an alternative to intubation. They are faster and easier to place and may reduce
201 the complications described above [20]. SADs are used safely, effectively and frequently in hospital procedures [21-
202 23]. They are now widespread in NHS ambulance services; in 2011/12 the London Ambulance Service reported 1,439
203 successful OHCA intubations, compared to 1,570 successful SAD placements[5]. Equipose between the two

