500 We will seek consent from survivors (or a consultee according to the requirements of the Mental Capacity Act 2005 if
501 the patient lacks capacity) to collect additional data at hospital discharge and 3 and 6 months after OHCA (depending
502 which consent option the participant chooses-see section 9.7.1). We have chosen a 6-month final follow-up because,
503 whilst there are very few additional deaths between 3 and 6 months, quality of life and functional independence in
504 activities of daily living continue to improve during this time [31].

505

506 *All enrolled patients*

- 507 1. Initial ventilation success, defined as visible chest rise.
- 508 2. Regurgitation/aspiration.
- 509 3. Loss of a previously established airway.
- 510 4. Actual sequence of airway interventions delivered.
- 511 5. Chest compression fraction (one ambulance region only, see below).
- 512 6. Return of spontaneous circulation (ROSC).
- 513 7. Airway management in place when ROSC was achieved or the resuscitation was discontinued.
- 514 8. Economic data regarding expenditure and further healthcare contacts.

515

516 *Patients who survive to admission to hospital (estimated 20% of enrolled patients)*

- 517 9. Length of intensive care stay.
- 518 10. Length of hospital stay.

519

520 *Patients who survive to hospital discharge (estimated 9% of enrolled patients)*

- 521 11. Quality of life (using the EQ-5D) at hospital discharge

522

523 *Patients who survive beyond hospital discharge*

- 524 12. Date of death (if applicable)
- 525 13. Modified Rankin scale at 3 and 6 months following OHCA
- 526 14. Quality of life (using the EQ-5D) at 3 and 6 months following OHCA.

527

528 Good quality, continuous CPR is associated with increased survival and improved neurological outcomes following
529 cardiac arrest [24, 32], and the concept of compression fraction has been developed as a standardised way of
530 measuring and expressing this [33]. The compression fraction is defined as the proportion (or percentage) of
531 resuscitation time without spontaneous circulation during which chest compressions are administered: the higher the
532 compression fraction the better the quality of CPR, and the more likely the patient is to survive [34]. Comparing the
533 compression fraction between the two randomisation arms may help to explain the study findings. Measuring and

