1678 or second attempt¹.
- 1679 2. Regurgitation/aspiration.
- 1680 3. Loss of a previously established airway.
- 1681 4. Actual sequence of airway interventions delivered.
- 1682 5. Chest compression fraction (two ambulance regions only, added part way through the trial)
- 1683 6. Return of spontaneous circulation (ROSC)*.
- 1684 7. Airway management in place when first ROSC was achieved or the resuscitation was discontinued.
- 1685

1686 Patients who survive to admission to hospital (estimated 20% of enrolled patients):

- 1687 8. Length of intensive care stay.
- 1688 9. Length of hospital stay.

¹ Note: chest rise and ETCO₂ is the definition on the CRF, but ETCO₂ is not included in the definition given in the protocol. Also, the protocol does not state whether success should be based on the first attempt only or the first or second attempt.

1689	
1690	Patients who survive to hospital discharge and consent to active follow-up (estimated 9% of enrolled
1691	patients):
1692	10. Quality of life (using the EQ-5D) at hospital discharge.
1693	
1694	Patients who survive beyond hospital discharge and consent to active follow-up:
1695	11. Time to death or last follow-up
1696	12. Modified Rankin score at 3 and 6 months following OHCA
1697	13. Quality of life (using the EQ-5D) at 3 and 6 months following OHCA.
1698	* note: this outcome includes both ROSC during advanced airway management attempts carried out by an
1699	AIRWAYS-2 paramedic and on ED arrival for those patients conveyed to ED
1700	2.5 Changes to the study objectives during the course of the study
1701	N/A
1702	2.6 Changes to the study outcomes during the course of the study
1703	There have been no outcomes added or removed, but outcomes that were not clearly defined in the protocol
1704	have been reviewed and precise definitions have been agreed. These include definitions for secondary
1705	outcomes 1 to 7, the addition of time to death as a more informative means of comparing length of ICU and
1706	hospital stays and two analyses of survival at 72h (as binary and time to event outcomes) . Definitions are
1707	given in Section 5.
1708	

1709 **3. STUDY POPULATION**

1710 The study population is patients aged 18 or over experiencing a non-traumatic OHCA. Enrolled patients must
1711 be attended by an A2 paramedic who is first or second at the patient's side and resuscitation must be

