1898 All outcomes listed in Sections 2.3 and 2.4 will be presented as per the template tables **Table T6** to **T8** and
1899 may also be presented graphically. General methods of presentation and assessing intervention effects are
1900 outlined below. For formal comparisons the intubation group will be the reference group. Details specific to
1901 each outcome are described as appropriate. Secondary outcomes 10 to 13 will not be reported in the primary
1902 outcome paper.

Date type	Outcomes
Binary	mRS (at discharge/30days) Initial ventilation success Regurgitation/aspiration Loss of previously established airway Return of spontaneous circulation (ROSC) 72h survival
Categorical	Actual sequence of airway interventions delivered ¹ Airway management in place when ROSC was achieved or resuscitation was discontinued or intervention from A2 paramedic stopped ¹
Continuous	Chest compression fraction

	Duration of ICU stay (presented separately for survivors and patients who die during ICU stay) ¹
	Duration of hospital stay (presented separately for survivors and patients who die during hospital stay) ¹
Time to event	Time from OHCA to when discharge/30 day mRS was assessed ^{1,3} Time to death ² Time to death (up to 72h)
Longitudinal	mRS (at discharge/30days, 3 months and 6 months) EQ-5D index score and visual analogue scale score (at discharge, 3 months and 6 months)

1903 *Note:-*

1904 ¹ These outcomes will be described but not formally compared

1905 ² Time to death will be formally compared in place of length of ICU and hospital stay

1906 ³ This is not a specified outcome but the DMSC raised it as a point of interest.

1907

1908 • **Binary outcomes** will be presented as numbers and percentages of patients in the category of interest.
1909 Outcomes will be compared between intervention groups using logistic regression. The intervention
1910 comparison estimate will be presented as an adjusted odds ratio (OR) with a 95% confidence interval
1911 (95% CI) and p-value. Formal statistical comparisons of treatment effects will only be performed if more
1912 than ten patients in total experience the outcome (with at least one event in each treatment group). .

1913 • **Categorical outcomes** will be presented as numbers and percentages of patients in each category.
1914 Outcomes will be compared between intervention groups using multinomial logistic regression.
1915 Treatment comparison estimates will be presented as adjusted odds ratios (OR) and 95% confidence

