Survived to hospital discharge						
Time to death (hours; median, IQR)					HR ³	
Time to death 0-72h (hours; median, IQR)					HR	
72 hour survival					OR	

2069 ¹OR=Odds ratio, HR=Hazard ratio

2070 ²ICC

2071 ³ ICC

2072

2073

2074

Table T7 Secondary outcomes and related post-intervention details

	Randomised to intubation (n=XX)		Randomised to i-gel (n=XX)		Estimate ¹ (95% CI)	p-value
	median	IQR	median	IQR		
Compression Fraction					MD/GMR	
	Randomised to intubation (n=XX)		Randomised to i-gel (n=XX)		Estimate ¹ (95% CI)	p-value
	n	%	n	%		
AIRWAY MANAGEMENT DETAILS						
Actual sequence of airway interventions delivered						
Sequence 1						
Sequence 2						
.....						
Initial ventilation success (first two attempts) of first advanced airway management						
Intubation						
I-gel						
Other SGA						
Total					OR	
Any ventilation success						
Intubation						
I-gel						
Other SGA						
Total					OR	
Any loss of previously established airway						
Intubation						
I-gel						
Other SGA						
Total					OR	
Regurgitation before initial i-gel/intubation attempt					OR	
If yes, aspiration					OR	
Regurgitation during or after initial i-gel/intubation attempt					OR	
If yes, aspiration					OR	
Any ROSC during advanced A2 airway management					OR	

[figure not shown]
Any ROSC during any A2 airway management						
Advanced airway management in place when patient first had ROSC						
Intubation						
I-gel						
Other SGA						
Other						
Airway management in place on final attempt by A2 paramedic in those who died on scene						
Intubation						
I-gel						
Other SGA						
Other						
Airway management in place when patient first had ROSC or on final attempt by A2 paramedic in those who died on scene						
Intubation						
I-gel						
Other SGA						
Other						
Total						
Airway management in place on final attempt by A2 paramedic in those who were admitted to ED						
Intubation						
I-gel						
Other SGA						
Other						
	Randomised to intubation (n=XX)		Randomised to i-gel (n=XX)		Estimate¹	
	n	%	n	%	(95% CI)	p-value
ED STAY						
Admitted to ED/ hospital						
ROSC on ED/hospital admission						
Survived to ED discharge						
ICU STAY						
Admitted to ICU from ED						
Survived to ICU discharge						
Duration of initial ICU stay in patients who survived to ICU discharge (hours; median, IQR)						

Duration of ICU stay in patients who died in ICU (hours; median, IQR)

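### Regurgitation/aspiration is listed as one binary outcome, but Table T7 tests it in four pieces, two of them conditional on regurgitation, and never compares the per-patient risk of any regurgitation or any aspiration

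*Protocol*

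**What the plan says.** - **Outcome as listed.** Protocol section 4.6.2 gives one item, "2. Regurgitation/aspiration", for all enrolled patients. SAP section 2.4 repeats it, and the outcome table in SAP section 6.2.2 puts "Regurgitation/aspiration" among the binary outcomes. For binary outcomes that section states: "Outcomes will be compared between intervention groups using logistic regression", with an adjusted odds ratio, confidence interval and p-value.
- **Definition promised.** SAP section 2.6 says that outcomes left unclear in the protocol "have been reviewed and precise definitions have been agreed. These include definitions for secondary" outcomes 1 to 7, and refers to Section 5. The Population 2 variables in SAP section 5.4 cover ventilation success, loss of airway, sequence of interventions and ROSC. None covers regurgitation or aspiration.
- **Definition as tabulated.** SAP Appendix A, Table T7 has "Regurgitation before initial i-gel/intubation attempt" and "Regurgitation during or after initial i-gel/intubation attempt". Below each is a row "If yes, aspiration". All four rows are marked for an OR.
- **Neighbouring rows.** In the same table, initial ventilation success, any ventilation success and loss of airway each end in a Total row, which carries the OR.
- **Population.** SAP section 3.7 assigns this outcome to Population 2, trial patients with at least one advanced airway attempt by the enrolling trial paramedic.
- **Expected direction.** Protocol section 9.3 expects regurgitation and aspiration to be possibly more common with the i-gel.

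**The concern.** The clinical question is which strategy leaves more patients with regurgitation, and which with aspiration. Table T7 tests neither.

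The aspiration rows compare only patients who regurgitated. Regurgitation happens after randomisation and may itself depend on the device, so this comparison does not have the protection of randomisation. If one device causes more regurgitation, the denominator changes with the device and the odds ratio can move away from the true difference in aspiration.

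The regurgitation rows cut one risk at the first i-gel or intubation attempt. If that moment comes at a different time in each arm, the same event can fall into different rows by arm.

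The stake is the formal comparison of a harm that the protocol itself anticipates. Serious adverse event reporting does not fill the gap: SAP sections 3.8 and 6.3 restrict it to unexpected, related events and plan no formal comparison.

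**Working it through.** **Plan's own figure.** The documents give no rate, power or sample size for regurgitation or aspiration, so there is nothing to reproduce. All percentages and times below are assumptions.

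**1. Aspiration conditional on regurgitation**

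Let r be the proportion who regurgitate and a the proportion of all patients who aspirate. The quantity in an aspiration row of T7 is a/r. The odds ratio of p1 vs p0 is [p1/(1−p1)] / [p0/(1−p0)]. One window is used for simplicity, and figures are i-gel vs intubation.

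| Regurgitation r | Aspiration per patient a | OR per patient | a/r | OR as in T7 |
|---|---|---|---|---|
| 25% vs 25% | 12.0% vs 12.0% | 1.00 | 48% vs 48% | 1.00 |
| 30% vs 25% | 15.0% vs 12.5% | 1.24 | 50% vs 50% | 1.00 |
| 30% vs 25% | 14.4% vs 12.5% | 1.18 | 48% vs 50% | 0.92 |
| 30% vs 25% | 12.0% vs 12.0% | 1.00 | 40% vs 48% | 0.72 |

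Second row: (0.150/0.850)/(0.125/0.875) = 0.1765/0.1429 = 1.24, while 0.50 vs 0.50 gives 1.00. Fourth row: (0.40/0.60)/(0.48/0.52) = 0.667/0.923 = 0.72.

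With equal regurgitation (first row) the two measures agree. Once regurgitation differs, the T7 measure can hide a difference, reverse it, or produce one where there is none.

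**2. Split at the first attempt**

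Assume 30 minutes at risk from arrival of the trial paramedic and one constant hazard λ in both arms, so there is no device effect. With total risk 25%, λ = −ln(0.75)/30 = 0.00959 per minute. If the first attempt starts at time t, the risk before it is 1−exp(−λt), and the risk of any episode during or after it is 1−exp(−λ(30−t)).

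| Start of first attempt, i-gel vs intubation | Before | OR | During or after | OR | Total OR |
|---|---|---|---|---|---|
| 5 vs 5 min | 4.7% vs 4.7% | 1.00 | 21.3% vs 21.3% | 1.00 | 1.00 |
| 2 vs 3 min | 1.9% vs 2.8% | 0.66 | 23.6% vs 22.8% | 1.04 | 1.00 |
| 3 vs 5 min | 2.8% vs 4.7% | 0.59 | 22.8% vs 21.3% | 1.09 | 1.00 |

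The distortion needs different start times. Under these assumptions it is large in the row before the attempt and modest in the row during or after it. The first of these also depends on when that window opens, which T7 does not say. Any earlier period common to both arms would pull its OR towards 1.

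**3. Text against text**

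SAP section 6.1 rules out tests on data that are not listed outcomes. If regurgitation before the attempt is only a comparability check, its OR in T7 conflicts with that rule. If it is part of outcome 2, the outcome is tested only in parts. The documents do not settle which is meant.

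**The case against.** **The split has a purpose.** Regurgitation before any attempt cannot be caused by the device, so separating it isolates the device-related period and gives a check on comparability in an unblinded cluster trial. This stands as a reason to show the split. It does not justify leaving out the total or testing aspiration only in those who regurgitated.

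**A single outcome may have been intended.** SAP section 6.2.2 names one binary outcome, and SAP section 1.4 calls the skeleton tables a guide whose layout may change. That is fair. However, section 1.4 also requires the content to stay consistent with Appendix A, and no combined variable is derived anywhere. The text needs reconciling.

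**A reader might infer that faster placement by itself produces opposite effects in the two windows.** The documents do not support this. Protocol section 2 says of supraglottic devices "They are faster and easier to place and may reduce" complications, which concerns insertion. The T7 boundary is the start of the attempt, and a shorter insertion does not move it. The rule in SAP section 3.5 on solo responders in the intubation arm does not settle the matter: where such a responder uses an i-gel first, that attempt opens the window. No start times are given for either arm.

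**A reader might also infer that the trial could not say which arm had more aspiration.** That goes too far. T7 prints counts by arm. With counts a1 and a2 in the two windows, the number with any aspiration lies between max(a1, a2) and a1 + a2. What is missing is the formal comparison.

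**Conclusion.** The concern holds in a limited form. Outcome 2 is listed as one binary outcome, has no derivation in SAP section 5, and is tested in Table T7 as four pieces with no per-patient comparison of any regurgitation or any aspiration.

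The firm part is the conditional aspiration test. Whenever regurgitation differs by arm, its OR need not reflect the difference in aspiration. In the illustrations it is 1.00 when the per-patient OR is 1.24, and 0.72 when the per-patient OR is 1.00. The mechanism follows from the table's structure, while the percentages are assumed.

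The distortion from the before/after split is a possibility of unknown size, because it depends on a difference in start times that the documents neither state nor exclude. The primary outcome is unaffected.

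**What to change.** In SAP section 5.4, derive two yes/no variables per patient, with all of Population 2 as denominator:

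- **Any regurgitation:** yes if recorded in either window; no if absent in both; otherwise missing.
- **Any aspiration:** yes if recorded in either window; no if, in each window, there was no regurgitation or regurgitation without aspiration; otherwise missing.

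In Table T7, compare these two by OR. Keep the before/after split and the conditional aspiration rows as counts and percentages, without OR or p-value.

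Population 2 is kept because SAP section 3.7 assigns it to this outcome. The case report form is not shown, so it cannot be confirmed that these items exist for patients without an advanced attempt.

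The cost is a change of wording in SAP section 5.4 and Table T7, using items that the existing T7 rows already require. The small downside is that events before the first attempt dilute a device-specific effect; the descriptive split still shows it.
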